9.7.1.2 Definitions of Analysis Sets

The Full Analysis Set (FAS) is the group of randomized subjects who received the study drug and had at least 1 evaluable postdose primary efficacy measurement.

The Per Protocol Analysis Set (PPS) is the group of subjects who sufficiently complied with the protocol. Details of the PPS criteria will be determined before database lock and unblinding and will be specified in the Statistical Analysis Plan.

The Safety Analysis Set is the group of subjects who received the study drug and had at least 1 evaluable postdose safety assessment.

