- Remission rates calculated based on remission criteria (DAS28-ESR, DAS28-CRP, SDAI, CDAI, and Boolean) at each evaluation time point
- Values and changes from baseline in modified total sharp score (mTSS) at each evaluation time point

< Analysis Sets >

- The Full Analysis Set (FAS) is the group of randomized subjects who received the study drug and had at least 1 evaluable postdose primary efficacy data.
- The Per Protocol Set (PPS) is the group of subjects who sufficiently complied with the protocol. Details of the PPS criteria will be determined before database lock and treatment unblinding and will be specified in the Statistical Analysis Plan.
- The Safety Analysis Set is the group of subjects who received at least 1 dose of study drug and had at least 1 evaluable postdose safety data.

< Efficacy Analyses >

The primary efficacy analysis set is FAS.

Analyses for the Primary Endpoint

ACR20 response rate at Week 12 will be analyzed using a logistic regression model with CRP level at the Screening Phase, disease duration and history of biologics treatment as covariates, for the comparison between placebo and either E6011 200 mg or 400 mg. Overall significance level is $\alpha=0.025$ (one-sided). The Hochberg method will be used to adjust the multiplicity. Subjects with missing primary efficacy endpoint due to early discontinuation or other reasons will be considered nonresponders. In case that the number of subjects in each category of covariates is very small, integration of the categories will be planned. ACR20 response rate and its 2-sided 95% confidence interval for each treatment group will be calculated. The difference in ACR20 response rate between each of E6011 doses and placebo and its 2-sided 95% confidence interval will also be calculated. Subgroup analyses or sensitivity analyses will be conducted as needed.

In addition, the following analyses will be conducted for ACR20 response rate at Week 12.

- To compare ACR20 response between E6011 100 mg and placebo by using a logistic regression model (CRP level at the Screening Phase, disease duration and history of biologics treatment as covariates). The difference in ACR20 response rate between E6011 100 mg and placebo and its 2-sided 95% confidence interval will also be calculated.
- To estimate the dose-response relationship using a statistical model, such as E_{max} model, if appropriate

Analyses for the Secondary Endpoints

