9.3.3 Removal of Subjects From Therapy or Assessment

The investigator or subinvestigator may withdraw the subject from the study at any time for safety or administrative reasons. The subject may stop study drug or withdraw from the study at any time for any reason.

All subjects who discontinue the study should be followed for procedures/assessments at discontinuation as specified in the Schedule of Procedures/Assessments ([Section 9.5.2.1, Table 4](#); also see [Section 9.5.5](#) “Completion/Discontinuation of Subjects” for more information).

A subject will be withdrawn from the study under any of the following circumstances.

1. Occurrence of AE that made it difficult to continue the study
2. Subject is pregnant.
3. Subject's ineligibility is confirmed.
4. Concomitant medication or therapy cannot be continued in accordance with the protocol.
5. Required surgical operation on arthritic disorder
6. Diagnosed with malignant tumor
7. Tested positive in tuberculosis test (QuantiFERON TB® Gold Test or T-SPOT®.TB Test)
8. Tested positive for any of the following: HIV, HBs antigen, HBV DNA, HCV antibody, HTLV-1 antibody, or syphilis (except if false positive for the syphilis test)
9. When the investigator or subinvestigator judges that efficacy of E6011 is insufficient, after the date Version 6 of the protocol was approved by IRB
10. When the investigator or subinvestigator judges that there are other effective treatment options available besides continuing this study, after the date Version 6 of the protocol was approved by IRB

Withdrawal from the study will be considered if a subject skips 3 consecutive administrations.

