9.5.1.3.1 ASSESSMENT OF TENDER AND SWOLLEN JOINT COUNTS

The number of tender joints and the number of swollen joints will be evaluated during the Screening and Observation Phases, Treatment Phase (Weeks 2, 4, 8, 12, 16, 20, and 24), Extension Phase (up to Week 104, every 4 weeks), and at discontinuation. As a general rule, assessments will be performed by the same investigator or subinvestigator at each site.

A total of 68 joints will be examined for tenderness by applying pressure to the joint or by moving joints. Tender joints will be marked with tick or cross in corresponding frames of the Assessment Sheet for Tender and Swollen Joint Counts (Appendix 7). A total of 66 joints (minus 2 hip joints) will be examined for swollen joints. Swollen joints will be marked with open circles in corresponding frames of the Assessment Sheet for Tender and Swollen Joint Counts (Appendix 7). If assessment cannot be made because the subject had a joint replacement procedure or due to any other reasons, a filled square will be entered.

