9.5.2 Schedule of Procedures/Assessments

9.5.2.1 Study Schedule

[Table 4](#) presents the schedule of procedures/assessments for this study.

Each assessment will be performed within 3 days before or after the scheduled date during Weeks 1 to 12 or within 7 days before or after the scheduled date after Week 14 using Week 0 as a reference point. In the Follow-up Phase, each assessment will be performed within 7 days before or after the scheduled date (“within 7 days after the scheduled date” for

the assessments at “70 days after the last dosing”). However, the interval between study treatments should be at least 3 days until 2 weeks after the start of study treatment, and at least 6 days after 4 weeks have elapsed since the start of study treatment. If any scheduled assessment or administration of the study drug cannot perform within the above period, each assessment will still be performed, but administration of the study drug will be skipped.

After the date Version 6 of the protocol is approved by IRB, it is unnecessary to conduct "tender and swollen joint counts/ESR", "VAS/HAQ", "RF/anti-CCP antibody/MMP-3", "serum E6011 concentration", "serum anti-E6011 antibody", "serum total FKN concentration", "cytokines/LRG1/Ang2", "TRACP-5b", "CX3CR1-positive cell count", or "VectraTM DA". However, assessments of "serum E6011 concentration" and "serum anti-E6011 antibody" will be conducted at discontinuation.

Table 4 Schedule of Procedures/Assessments in Study E6011-J081-201

Phase	Screen-ing	Obser-vation	Treatment							
			W0		W1	W2	W4	W6	W8	W10
Assessment	Time postdose Day -42 to Day -1	Day 1		Day 8 ±3 days	Day 15 ±3 days	Day 29 ±3 days	Day 43 ±3 days	Day 57 ±3 days	Day 71 ±3 days	Day 85 ±3 days
		Pre	Dosing							
Informed consent	X									
Demographics, medical history, complication	X									
Inclusion/exclusion criteria	X	X								
Study drug administration ^a			X	X	X	X	X	X	X	X
Prior treatment / concomitant medication or therapy										
Vital signs	X	X		X	X	X		X		X
Height / body weight ^b	X ^b									X
Physical findings, injection site finding ^c	X	X		X	X	X		X		X
Standard 12-lead ECG		X								X
Chest x-ray	X									X
Pregnancy test ^d	X	X ^d								X
Neurological findings ^e	X									X
Anti-JCV antibody test	X									
Blood CD4-positive cells	X									X
Viral test, syphilis test, TB test	X									
Number of tender / swollen joints, ESR	X	X			X	X		X		X
VAS, HAQ		X			X	X		X		X
Joint x-ray	X									

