9.7.1.1 Study Endpoints

9.7.1.1.1 PRIMARY ENDPOINT

- ACR20 response rate at Week 12

ACR20 response rate: A subject is defined as ACR20 responder if all of the following 3 criteria are met, and ACR 20 response rate refers to the percentage of subjects with ACR20 response:

1. Greater than or equal to 20% reduction from baseline in the tender joint counts (out of 68 joints)
2. Greater than or equal to 20% reduction from baseline in the swollen joint counts (out of 66 joints)
3. Greater than or equal to 20% reduction from baseline in at least 3 of the following 5 assessments:
 - Physician's disease activity assessment
 - Patient's disease activity assessment
 - Patient's pain assessment
 - HAQ
 - CRP

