9.7.1.6 Efficacy Analyses

The FAS will be used as the primary population for the efficacy analyses, while the PPS will be used as a supportive population for the efficacy analyses.

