9.7.1.6.1 PRIMARY EFFICACY ANALYSIS

ACR20 response rate at Week 12 will be analyzed using a logistic regression model with CRP level at the Screening Phase, disease duration and history of biologics treatment as covariates, for the comparison between placebo and either E6011 200 mg or 400 mg. Overall significance level is $\alpha=0.025$ (one-sided). The Hochberg method will be used to adjust the multiplicity. Subjects with missing primary efficacy endpoint due to early discontinuation or other reasons will be considered nonresponders. In case that the number of subjects in each category of covariates is very small, integration of the categories will be planned. ACR20 response rate and its 2-sided 95% confidence interval for each treatment group will be calculated. The difference in ACR20 response rate between each of E6011 doses and placebo and its 2-sided 95% confidence interval will also be calculated. Subgroup analyses or sensitivity analyses will be conducted as needed.

In addition, the following analyses will be conducted for ACR20 response rate at Week 12.

- To compare ACR20 response between E6011 100 mg and placebo using a logistic regression model with CRP level at the Screening Phase, disease duration and history of biologics treatment as covariates. The difference in ACR20 response rate between E6011 100 mg and placebo and its 2-sided 95% confidence interval will also be calculated.
- To estimate the dose-response relationship using a statistical model, such as E_{max} model, if appropriate.

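### The primary-analysis FAS drops a dosed subject with no post-dose ACR assessment, although the non-responder rule could classify that subject; few are likely to be affected

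*Protocol*

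**What the plan says.** - **Analysis set.** Protocol 9.7.1.2 defines the FAS as "randomized subjects who received the study drug and had at least 1 evaluable postdose primary efficacy measurement". The synopsis has the same condition: "had at least 1 evaluable postdose primary efficacy data".
- **Role of the set.** Protocol 9.7.1.6: "The FAS will be used as the primary population for the efficacy analyses".
- **Missing primary endpoint.** Protocol 9.7.1.6.1: "Subjects with missing primary efficacy endpoint due to early discontinuation or other reasons will be considered nonresponders". The same section allows sensitivity analyses as needed but names none on all dosed subjects.
- **Endpoint.** ACR20 (9.7.1.1.1) requires improvement in tender and swollen joint counts plus "Greater than or equal to 20% reduction from baseline in at least 3 of the following 5 assessments".
- **When components are measured.** Sections 9.5.1.3.1 to 9.5.1.3.5 schedule them from Week 2 onwards and again when a subject stops; for joint counts the schedule ends with "Extension Phase (up to Week 104, every 4 weeks), and at discontinuation".
- **Early stoppers.** Section 9.3.3: "All subjects who discontinue the study should be followed for procedures/assessments at discontinuation". Section 9.5.5 adds mail or telephone contact for subjects who no longer attend; the items it lists include no ACR component.
- **Late visits.** Section 9.5.2.1: "each assessment will still be performed, but administration of the study drug will be skipped".

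The SAP supplied covers the Extension Phase, has a different FAS (SAP 5.2.1) and plans no primary efficacy analysis (SAP 5.4.1). The Treatment Phase SAP announced in Protocol 9.7 was not available.

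**The concern.** The two rules do not fit together. Non-responder imputation exists so that a binary endpoint can be assigned to every subject, whatever was or was not observed. Requiring a post-dose measurement for entry to the analysis set then takes away the subjects for whom the rule matters most. It is a post-randomisation exclusion that the endpoint does not need.

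The direction within an arm is fixed. The excluded subject would have counted as a non-responder, so leaving that subject out raises the observed ACR20 rate. If both arms lose the same number, a true benefit is slightly enlarged. If the arms lose different numbers, the comparison shifts towards the arm with more losses.

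**Working it through.** **Reading of the definition.** The protocol does not define a primary efficacy measurement. I read it as any post-dose measurement of the ACR components. Read literally as the Week 12 ACR20 result, it would exclude everyone missing Week 12, and the non-responder rule would have almost nothing to act on.

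**Who is left out.** Anyone assessed at Week 2 or later, or at a discontinuation visit, is in the FAS and becomes a non-responder if Week 12 is missing. What remains is mainly the subject who stops returning before Week 2.

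**Inputs.** From Protocol 9.7.2: 50 per arm, 30% placebo, 60% active, one-sided 0.0125, chi-square test. The documents give no number of subjects without a post-dose assessment, so I assume 1, 2 or 3 of 50 per arm.

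**The plan's own power.** The pooled chi-square normal approximation gives 0.911 for 65% vs 30% and 0.791 for 60% vs 30%. The stated 91% and 79% are reproduced.

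**Effect on the difference.** Take 30/50 and 15/50 responders when all dosed subjects count, with a active and b placebo subjects excluded:

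FAS difference = 30/(50 − a) − 15/(50 − b)

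For a = b = 2: 30/48 − 15/48 = 62.5% − 31.25% = 31.25 points.

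| Excluded | Equal in both arms | Active only | Placebo only |
|---|---|---|---|
| 0 | 30.0 | 30.0 | 30.0 |
| 1 | 30.6 | 31.2 | 29.4 |
| 2 | 31.25 | 32.5 | 28.75 |
| 3 | 31.9 | 33.8 | 28.1 |

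**Type I error.** Pooled one-sided z test at nominal 0.0125, full enumeration of two binomials of size 50 − a and 50 − b. With no loss it is 0.0123.

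- Null A, 30% response among assessed subjects in both arms: 0.0120 to 0.0133 over all the loss patterns above, equal or one-sided.
- Null B, 30% response among all dosed subjects in both arms, so the assessed rate is 15/(50 − k) in an arm that loses k:

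| Excluded | Equal | Active only | Placebo only |
|---|---|---|---|
| 1 | 0.0121 | 0.0151 | 0.0103 |
| 2 | 0.0130 | 0.0186 | 0.0089 |
| 3 | 0.0126 | 0.0200 | 0.0078 |

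Inflation therefore needs both losses concentrated in the active arm and a null stated on the all-dosed rate.

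**Power.** Same enumeration, now with 60% and 30% taken as rates among assessed subjects, so responders are Bin(50 − k, 0.6) and Bin(50 − k, 0.3):

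| k per arm | Current FAS (denominator 50 − k) | All dosed (denominator 50) |
|---|---|---|
| 0 | 0.781 | 0.781 |
| 1 | 0.776 | 0.767 |
| 2 | 0.800 | 0.753 |
| 3 | 0.784 | 0.739 |

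The FAS column is not monotone because the test is discrete. The smooth approximation for k = 1, 2, 3 gives 0.782, 0.773, 0.763 (FAS) against 0.774, 0.757, 0.739 (all dosed). If 60% and 30% are instead the all-dosed rates, the all-dosed analysis loses no power: the enumeration gives 0.783, 0.785, 0.787.

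These figures describe one unadjusted comparison at the planning level, not the planned logistic model or the Hochberg family-wise rate.

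**The case against.** The strongest reply is that there may be no affected subject at all. Assessments begin at Week 2 and are repeated on stopping, and late assessments are still made, so almost nobody can fall outside the FAS. The upper end of the assumed range, 3 of 50, is generous. The one-arm scenarios have no support either: the Treatment Phase is double-blind (9.4.6) and every arm receives 4 mL through Week 10 (9.4.1). Under equal losses the difference moves by 0.6 to 1.9 points, which is unlikely to change a conclusion. Section 9.7.1.6.1 leaves room for sensitivity analyses, and the Treatment Phase SAP may specify one. Sections 9.7.1.3 and 9.7.1.4 report disposition by group and baseline data for both the safety set and the FAS, so a reader could largely see the exclusions.

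Most of this stands, and it limits the point to a minor one. It does not remove it. The general allowance for sensitivity analyses commits to nothing specific, and disposition and baseline tables give neither an all-dosed estimate nor an explicit count of FAS exclusions. What the unsupplied SAP says cannot be assumed in either direction.

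**Conclusion.** The concern holds, at the low end of minor. The FAS definition and the non-responder rule are inconsistent in purpose, and the result is an avoidable exclusion after randomisation.

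The likely size is small: with 1 to 3 equal losses per arm, the apparent benefit is overstated by 0.6 to 1.9 points and type I error stays close to its no-loss value. The larger shifts, up to 33.8 points or a type I error of 0.0200, are worst cases that require all losses in the active arm; the error figure also requires the all-dosed null.

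The conclusion assumes that the primary efficacy measurement means any post-dose ACR component. The numbers rest on an assumed range of losses. The Treatment Phase SAP could already resolve the matter.

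**What to change.** For ACR20 at Week 12 and the other binary Treatment Phase endpoints, define the analysis set in Protocol 9.7.1.2 and the synopsis as all randomised subjects who received at least one dose, analysed as randomised. Count every missing response as non-response, including where no post-dose assessment exists. Keep the present FAS as a named sensitivity set, report exclusions by arm, and align the Treatment Phase SAP.

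This may no longer be possible. Protocol section 7 says the last subject entered the Extension Phase in March 2018, so the Treatment Phase database may be locked. In that case leave the primary set unchanged and report the all-dosed analysis as a labelled sensitivity analysis.

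The cost is wording, or one extra table; no new data or visits are needed. Observed response rates fall slightly, and power may fall as shown in the working. If losses did differ between arms, the all-dosed analysis would treat them as treatment failure, which is a reason to show both sets.

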9.7.1.3 Subject Disposition

The number of subjects who provided signed informed consent, and who failed screening along with the reason for such screen failure will be summarized.

The number of randomized subjects, subjects who are treated/not treated (after randomization), completed/discontinued the study, and the reason for the discontinuation will be summarized for each treatment group and the overall subjects.

9.7.1.4 Demographic and Other Baseline Characteristics

Demographic and other baseline characteristics for the Safety Analysis Set and FAS will be summarized for each treatment group and the overall subjects. Continuous variables include age, RA duration; categorical variables include sex, race, etc.

9.7.1.5 Prior and Concomitant Therapy

All investigator terms for medications recorded in the CRF will be coded to an 11-digit code using the World Health Organization Drug Dictionary (WHO DD). The number (percentage) of subjects who took prior and concomitant medications will be summarized on the FAS by treatment group, Anatomical Therapeutic Chemical (ATC) class, and WHO DD preferred term. Prior medications will be defined as medications that stopped before the first dose of study drug. Concomitant medications will be defined as medications that (1) started before the first dose of study drug and were continuing at the time of the first dose of study drug, or (2) started on or after the date of the first dose of study drug. All medications will be presented in subject data listings.

9.7.1.6 Efficacy Analyses

The FAS will be used as the primary population for the efficacy analyses, while the PPS will be used as a supportive population for the efficacy analyses.

9.7.1.6.1 PRIMARY EFFICACY ANALYSIS

ACR20 response rate at Week 12 will be analyzed using a logistic regression model with CRP level at the Screening Phase, disease duration and history of biologics treatment as covariates, for the comparison between placebo and either E6011 200 mg or 400 mg. Overall significance level is $\alpha=0.025$ (one-sided). The Hochberg method will be used to adjust the multiplicity. Subjects with missing primary efficacy endpoint due to early discontinuation or other reasons will be considered nonresponders. In case that the number of subjects in each category of covariates is very small, integration of the categories will be planned. ACR20 response rate and its 2-sided 95% confidence interval for each treatment group will be calculated. The difference in ACR20 response rate between each of E6011 doses and placebo and its 2-sided 95% confidence interval will also be calculated. Subgroup analyses or sensitivity analyses will be conducted as needed.

In addition, the following analyses will be conducted for ACR20 response rate at Week 12.

- To compare ACR20 response between E6011 100 mg and placebo using a logistic regression model with CRP level at the Screening Phase, disease duration and history of biologics treatment as covariates. The difference in ACR20 response rate between E6011 100 mg and placebo and its 2-sided 95% confidence interval will also be calculated.
- To estimate the dose-response relationship using a statistical model, such as E_{max} model, if appropriate.

9.7.1.6.2 SECONDARY EFFICACY ANALYSES

The multiplicity adjustment will not be considered for secondary efficacy analyses.

For ACR20 (excluding Week 12), ACR50, and ACR70 response rates at each time evaluation time point, similar analyses to primary analyses will be conducted.

For each component of ACR (number of tender joints, number of swollen joints, VAS [patient's pain assessment and patient's disease activity global assessment, and physician's disease activity global assessment], patient's physical function assessment [HAQ] and CRP/ESR), DAS28-ESR, DAS28-CRP, SDAI, and CDAI in each evaluation time point, summary statistics (mean, standard deviation, median, and range) for the values and the changes from baseline will be calculated by treatment group and evaluation time point. The changes from baseline will also be analyzed using ANCOVA with baseline value, CRP level at the Screening Phase, disease duration and history of biologics treatment as covariates. The significance level for comparisons between placebo and each treatment group with E6011 (100 mg, 200 mg, and 400 mg) is $\alpha=0.05$ (2-sided).

For mTSS, summary statistics for values and change from baseline will be calculated by treatment group and evaluation time point. The changes from baseline will be analyzed using ANCOVA in the same manner as above.

For EULAR response classification and disease activity classification based on DAS28-ESR and DAS28-CRP, shift tables will be created by treatment group and evaluation time point.

For remission rates calculated based on remission criteria (DAS28-ESR, DAS28-CRP, SDAI, CDAI, and Boolean), similar analyses to primary analyses will be conducted.

